### **c Aim, objectives and Hypotheses:**

Aim and objectives:

The aim of this study is to evaluate the cost-effectiveness of the RAMP-HT of the HA in primary care patients with uncontrolled hypertension.

The objectives are to

1. Evaluate the long term (5-year) effectiveness of RAMP-HT compared to usual care in reducing cardiovascular complications, end-stage renal disease and all-cause mortalities in a cohort of primary care patients with uncontrolled hypertension at baseline
2. Estimate the direct medical cost of RAMP-HT and other health services

among primary care HT patients with or without complications

3. Evaluate the cost-effectiveness of RAMP-HT, compared to usual care, in gaining one Quality-Adjusted Life Year (QALY) in primary care patients with uncontrolled hypertension

Hypotheses:

1. RAMP-HT is more effective in reducing 5-year cardiovascular complications, end stage renal disease and all-cause mortality among primary care patients with uncontrolled hypertension compared to usual care
2. The direct medical cost of RAMP-HT patients, for the same disease complication status, is not higher than that of usual care except for the RAMP-HT cost
3. The direct medical cost of HT patients with one or more complications is higher than that of HT patients without any complication
4. RAMP-HT is cost-effective compared to usual care, i.e. the incremental cost-effectiveness ratio (ICER) per QALY gained is below the threshold value of 1 annual GDP (Gross Domestic Product) per capita of Hong Kong (HK\$295,303, 2013), which is the benchmark recommended by the World Health Organization

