#### *Sample size calculation*

- a. For the long-term effectiveness evaluation, the difference in 5-year incidence of CVD between the RAMP-HT and usual care group is the primary outcome. From the result of our RAMP-HT QOC study, the observed 1-year incidence of CVD in the RAMP-HT and usual care group was 1.33% and 1.76% respectively. A conservative estimate of the 5-year incidence of CVD in RAMP-HT and usual care group would be 7% and 8%, respectively. A minimum sample size of 7,116 subjects from each group will be needed to detect a difference of 1% in incidence rates of CVD between RAMP-HT and usual care group with 90% power and at 5% level of significance.

We have identified from the HA CMS data set of the RAMP-HT QOC study 8,681 eligible RAMP-HT patients and 8,681 usual care patients who fulfilled the inclusion criteria and without any exclusion criterion matched by propensity score matching. These two matched cohorts will be the subjects of this long-term effectiveness and cost-effectiveness

study. The flow chart of subject selection is attached in Appendix C.

- b. For the costing analysis, 140 subjects from each of the RAMP-HT and usual care groups will be required to show that the direct medical costs of RAMP-HT patients (excluding RAMP cost) is not higher than that of usual care HT patients by independent one side t-test with 0.3 effect size and 80% power at 5% significance level.

307 RAMP-HT and 291 usual care patients had been recruited from May 2013 to March 2014 in GOPCs across Hong Kong for the longitudinal evaluation of patient reported outcomes (PRO) in the RAMP-HT QOC study. These patients will be follow-up from May 2015 to March 2016 as part of our RAMP-HT QOC study; telephone survey on private health service utilization will be conducted at the same time. Taking 25% attrition rate into account, 230 RAMP-HT and 218 usual care patients will complete the questionnaire. This sample will be adequate for the comparison of private medical cost between RAMP-HT and usual care group.

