### (iii) Outcome Measures

The primary outcomes of this study are:

1. The 5-year incidence of CVD among RAMP-HT and usual care HT patients
2. The direct medical costs of RAMP-HT and usual care HT patients with and without complications
3. The ICER of cost per QALY gained by RAMP-HT compared to usual care group

The secondary outcomes of this study are:

4. The 5-year incidence of end stage renal disease (ESRD) and all-cause mortality among RAMP-HT and usual care HT patients
5. The hazard ratio of CVD, ESRD and all-cause mortalities between

RAMP-HT and usual care group

6. The Number-Need-to-Treat (NNT) to reduce one CVD, ESRD and mortality in 5 years by RAMP-HT

(iv) Data Collection

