#### *(i) In-depth costing of RAMP-HT*

The cost of RAMP-HT comprises of three components: (a) set-up costs; (b) ongoing intervention costs; and (c) central administrative costs. Set-up costs refer to one-off expenses incurred in the course of setting up the programme, which include costs related to staff training, additional equipment, information technology and infrastructure. Ongoing intervention costs refer to the recurrent costs for the programme operation and maintenance, which include costs of staff, printing and consumables in the clinics. The evaluation of the set-up costs will be primarily based on the data reported by the clusters, who are responsible for maintaining detailed inventory of supplies purchased and distributed to the clinics. Central administrative costs refer to recurrent costs incurred by the GOPCs for running RAMP-HT (i.e. project team cost in Head Office).

The set-up and intervention costs will be collected by two sets of questionnaires to be completed by RAMP-HT programme co-ordinators of the HA clusters and GOPCs that provide the RAMP-HT service (Appendix D); The central administration costs will be collected from the Finance Office in HA Head Office by a structured questionnaire. These questionnaires are adapted from the costing questionnaires that were used in our in-depth study on the cost-effectiveness analysis of RAMP-DM that had proven feasibility and validity (HHSRF # EPC\_HKU-1A).

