**Long Term Effectiveness of RAMP-HT**

Descriptive statistics will be performed on the clinical parameters (e.g. blood pressure (BP), lipid profile, BMI) and incidence of CHD, heart failure, stroke, ESRD, HT-related mortality and all-cause mortalities of the RAMP-HT and usual care cohorts. Differences in each outcome between groups will be tested using independent t-tests for continuous variables such as mean BP, or chi-square tests for categorical variables such as proportion of patients with BP control or CVD incidence. The number needed to treat to reduce one CVD, each specific HT complication and death by RAMP-HT will be calculated from the unadjusted 5-year rates between RAMP-HT and usual care HT cohorts.

Multivariable Cox proportional hazards regression will be performed to estimate the adjusted effect of RAMP-HT on the dependent variable of each first HT complication event, adjusting for all baseline covariates of patients. Cox model has been widely used to evaluate the effectiveness of primary care intervention in previous study. For each model, survival curves will be estimated by Kaplan-Meier method and the differences between RAMP-HT and usual care groups will be compared using the

log-rank test. The effectiveness of RAMP-HT will be measured by Hazard ratio with 95% confidence intervals in the regression models. Predictive accuracy of Cox models will be assessed and compared using Harrell's discrimination C-index, ranging from zero to one. A value of 0.5 indicates no predictive discrimination, and values of 0 or 1.0 indicate perfect separation of patients. Goodness-of-fit for Cox regression model will be assessed using Akaike information criterion and Bayesian information criterion.

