#### **Cost Effectiveness Analysis of RAMP-HT by Markov Modeling**

To evaluate the long term cost-effectiveness of RAMP-HT, a Markov model will be developed based on the natural history of a patient population, with similar distribution of age and gender as the RAMP-HT cohort, to simulate disease development over a lifetime. The structure of the model will be established as shown in Figure 1. At the end of each year, each HT subject may die, develop one HT complication or stay alive without complications. For subjects who develop complications, they may die immediately from the complication, die from other cause of death or stay alive in the complication health state.

The transition probabilities of developing complications and death from year to year will be estimated from the observed complication rates from the 5-year cohort study for RAMP-HT and usual care HT patients as described above. HT complication related mortality rates will be estimated by a review of published and unpublished local and overseas literature. Hong Kong standard life table will be used as a benchmark of survival presenting HT related mortality and mortality from other causes in Hong Kong local population among different demographic groups (e.g. age and sex). The cumulated life-years of the RAMP-HT and usual care cohorts will be calculated. The average cost and preference values for each HT disease state (with or without specific complication) obtained from the cost and

preference studies described above will be applied to the model to determine the cumulative quality adjusted life years (QALY) and lifetime costs for RAMP-HT and usual care cohorts.

The measure of cost-effectiveness of RAMP-HT will be the incremental cost-effectiveness ratio (ICER) in term of cost per QALY gained by RAMP-HT group compared to usual care. By comparing the between-group-differences in average lifetime costs ( $\Delta C$ ) and quality adjusted life years (QALYs) gained ( $\Delta E$ ), the ICER will be calculated by dividing the incremental cost ( $\Delta C$ ) by the incremental effectiveness ( $\Delta E$ ) in terms of QALYs gained by the RAMP-HT intervention compared to usual care. The ICER will be compared against the threshold value of 1 GDP (Gross Domestic Product) per capita of Hong Kong / QALY (HK\$295,303, 20137) to determine lifetime cost effectiveness of RAMP-HT.

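### The cost-effectiveness verdict (Hypothesis 4, primary outcome 3) rests on one point ICER compared with HK$295,303, and no planned analysis carries the uncertainty of the inputs into it

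*Combined protocol and SAP*

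**What the plan says.** All references are to the combined protocol and SAP.

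- **Outcome Measures**, primary outcome 3: "The ICER of cost per QALY gained by RAMP-HT compared to usual care group".
- **Aim, objectives and Hypotheses**, Hypothesis 4: RAMP-HT counts as cost-effective if "the incremental cost-effectiveness ratio (ICER) per QALY gained is below the threshold value of 1 annual GDP" per capita.
- **Cost Effectiveness Analysis of RAMP-HT by Markov Modeling**: the ICER is one ratio, the difference in average lifetime cost divided by the difference in average QALYs. Then "The ICER will be compared against the threshold value of 1 GDP (Gross Domestic Product) per capita of Hong Kong / QALY", given as HK$295,303.
- **Markov assumptions** (list after the data sources table): one complication per lifetime (item 1); an effect in years 1 to 5 only (item 4); repeat every 12 to 24 months without waning, with the average interval taken from empirical data (item 5); equal costs within a health state apart from the programme cost (item 6); 3.5% discounting (item 7). Each is a single scenario.
- **Long Term Effectiveness of RAMP-HT**: Cox models estimate "the adjusted effect of RAMP-HT on the dependent variable of each first HT complication event", reported as hazard ratios with 95% confidence intervals. Nothing says that these intervals enter the Markov model.
- **Table 1** lists the model inputs without ranges or distributions.

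**The concern.** Nearly every model input is an estimate. The hazard ratios and event rates come from the matched cohorts. Mortality after a complication comes from a literature review. Private costs come from an expected 230 + 218 survey responders. SF-6D values come from a few hundred patients divided among the five health states of Table 1. For the programme cost, "The set-up and intervention costs will be collected by two sets of questionnaires", with central costs from a third. The 0.7 factor applied to clinic attendance costs is a single fixed value.

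The planned rule uses none of this uncertainty. It returns cost-effective or not cost-effective according to the side of HK$295,303 on which one number falls. The section on purpose and potential says that the results can inform policy on whether such programmes should be implemented. A policy reader would need to know how firmly the data support the verdict, and the plan produces nothing that says so.

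**Working it through.** **What can be reproduced.** The plan gives no ICER, programme cost, state cost, utility or mortality rate, so it holds no cost-effectiveness figure to reproduce. What can be checked is how precisely the planned cohort would estimate the effect that drives the ICER.

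**Inputs**, all from Sample size calculation: "A conservative estimate of the 5-year incidence of CVD in RAMP-HT and usual care group would be 7% and 8%, respectively"; 8,681 matched patients per group; and, for a favourable case, "the observed 1-year incidence of CVD in the RAMP-HT and usual care group was 1.33% and 1.76% respectively".

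**Step 1. Hazard ratio and its precision, planned case.**
- HR = ln(0.93)/ln(0.92) = 0.870.
- Expected events: 0.07 × 8,681 = 607.7 and 0.08 × 8,681 = 694.5.
- SE(ln HR) = √(1/607.7 + 1/694.5) = 0.0555.
- 95% CI = exp(ln 0.870 ± 1.96 × 0.0555) = 0.781 to 0.970.

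**Step 2. CVD events averted over 5 years.** Averted = 0.08 − (1 − 0.92^HR).

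| HR | Averted per 1,000 | Patients per event averted |
|---|---|---|
| 0.781 | 17.0 | 58.9 |
| 0.870 | 10.0 | 100 |
| 0.970 | 2.3 | 440.6 |

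At any fixed repeat interval, patients treated per event averted span 440.6/58.9 = 7.5-fold. As a cross-check, the risk difference has SE √(0.07 × 0.93/8,681 + 0.08 × 0.92/8,681) = 0.0040. That gives 1.00 percentage point (0.22 to 1.78), in line with the table.

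**Step 3. Link to the verdict.** Under items 4 and 6 the arms differ only through the hazard ratio in years 1 to 5 and the programme cost. With the other inputs fixed, the verdict therefore turns on a break-even number of events averted, A\*. The corresponding hazard ratio is HR\* = ln(1 − (0.08 − A\*))/ln(0.92). If the estimate equals the assumed HR, the share of its sampling distribution on the wrong side of break-even is 1 − Φ((ln HR\* − ln HR)/SE). The values of A\* below are assumptions.

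**Step 4. Favourable case.** If the 1-year ratio persisted:
- HR = ln(1 − 0.0133)/ln(1 − 0.0176) = 0.754.
- With 8% in usual care, events are 529.0 and 694.5, so SE = 0.0577.
- Events averted = 19.06 per 1,000.

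| Break-even per 1,000 (assumed) | HR\* | Planned case, HR 0.870 | Favourable case, HR 0.754 |
|---|---|---|---|
| 5.0 | 0.935 | 9.9% | 0.01% |
| 7.5 | 0.903 | 25.6% | 0.09% |
| 9.0 | 0.883 | 39.6% | 0.3% |

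Break-even depends on costs and QALYs and not on the effect observed, so both columns use the same values. Values of 0.5%, 9% and 29% arise in the favourable case only if break-even is set at 50%, 75% or 90% of 19.06, that is 9.5, 14.3 or 17.2 per 1,000.

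The calculation assumes full 5-year follow-up and net benefit proportional to CVD events averted. It makes no allowance for ESRD (no rate is given), covariate adjustment or pairing.

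**The case against.** The strongest reply is that nothing shows this particular verdict to be fragile. The documents do not place break-even anywhere, and a value of 9.0 against a planned 10.0 puts the result beside the threshold by construction. The plan itself calls 7% versus 8% conservative. If the only effect already observed persisted, hazard-ratio error would hardly matter at the same break-evens. All of this stands. A reader might infer that the ICER conclusion is likely to be wrong, and the documents do not support that.

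Three other strong readings also fail.
- A reader might infer that the plan quantifies no uncertainty at all. The hazard ratio does get a 95% confidence interval; what is missing is its passage into the ICER.
- A reader might multiply the hazard-ratio limits by the whole 12 to 24 month repeat range to obtain a much wider spread. Item 5 replaces that range with an empirical average. Set-up and central administrative costs also need not scale with the number of rounds.
- A reader might suspect that an uncertainty analysis sits in material not supplied. Figure 1 and the appendices are not shown, but the analysis section, the assumptions and Table 1 are, and no listed appendix title concerns sensitivity analysis.

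It can also be said that this is a short funding proposal and that the analysis could be added later. That limits the severity. It does not remove the reason to fix distributions and scenarios before the ICER is known.

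**Conclusion.** The point holds as an omission in the decision rule. A primary outcome and a hypothesis are settled by a point ICER against HK$295,303, with no measure of how well the data support the answer. This follows from the text alone and does not depend on the illustration.

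The practical size is unknown, because no ICER can be computed. Under the plan's conservative effect and an assumed break-even of 5.0 to 9.0 events averted per 1,000, hazard-ratio error alone leaves about a 10% to 40% chance that a cost-effective verdict is not supported. Under the observed 1-year ratio, the chance at the same break-evens is about 0.01% to 0.3%. Uncertainty in costs, utilities, mortality and model structure would come on top and cannot be sized from the documents. The change should be made; the planned base-case ICER itself can stand.

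**What to change.** In the Markov modelling section, keep the base-case ICER and add the following, fixed before the preliminary ICER on 3-year data in the Timeline:

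1. A probabilistic sensitivity analysis of the planned Markov model, with distributions for the hazard ratios, baseline event rates, complication mortality, state costs, SF-6D utilities and RAMP-HT programme cost.
2. Alongside the ICER, the incremental net benefit at HK$295,303 with a 95% interval, and the probability of cost-effectiveness.
3. Scenario analyses for the 5-year effect duration, the one-complication assumption, the 0.7 manpower factor, equal state costs (item 6, using the by-arm costs already planned in the Cost Analysis section) and the 3.5% discount rate.
4. A Hypothesis 4 conclusion worded from these results and not from the point ICER alone.

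Two passages need reconciling before the distributions are set.
- The Markov section takes transition probabilities from observed rates in both cohorts, whereas item 4 and the Table 1 footnote apply a hazard ratio to the transition probabilities.
- The data sources table gives 410 + 388 patients with SF-12v2 data. Sample size calculation and Direct Medical Costs of HT patients give 307 + 291 recruited for the patient-reported outcome study over the same months.

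The cost is SAP wording and some days of modelling. Standard errors must be kept for sampled inputs, and ranges recorded in the literature review and the cost questionnaires. No new patient data are needed. The price is that the verdict may become less definite.

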### **Cost Analysis of RAMP-HT**

Descriptive statistics will be used to summarize the costs of RAMP-HT and annual direct medical costs for RAMP-HT and usual care patients at baseline and over each of 5 subsequent years, overall, and by the presence of complications. The cost of each healthcare service will be derived by multiplication of the unit cost from Gazette and Hospital Authority ordinance and the number of respective services used by the patients. To avoid double counting the cost of drugs and laboratory tests, the Government Gazette cost of each GOPC and SOPC attendance will be adjusted by a factor of 0.7 to include only the manpower cost. The total public medical costs will be calculated by summing up all costs of drugs, laboratory tests and each healthcare service utilisation. The private medical costs will be estimated by summarizing the self-reported costs of private consultations, self-medication and private hospitalisation. The average annual public and private direct medical costs per patient will be analysed by HT complication status (CHD, heart failure, stroke and ESRD), and by RAMP-HT and usual care HT groups. To determine whether the direct medical costs of the RAMP-HT cohort is higher than the usual care HT cohort, one sided independent t-test will be performed.

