3. HT patients with complications may die from either HT-related death or other cause of death.
4. RAMP-HT is effective in reducing HT complications for a period of 5 year; thus the transition probability adjustment of CVD/ESRD development (as determined by the annualized hazard ratio obtained from our long-term effectiveness analysis) will be applied to the model of the RAMP-HT cohort in the first five years. After 5 years, the RAMP-HT will have the same transition probabilities of developing HT complications as usual care HT cohort.
5. RAMP-HT is repeated every 12-24 months and the effectiveness of RAMP-HT will not decrease over time; thus the 5-year effect of RAMP-HT can be annualized. Adjustment will be made on the average duration of repeat RAMP-HT based on available empirical data in order to avoid over-estimation of the RAMP-HT cost.
6. The medical cost (public and private) of HT patients in usual care and RAMP-HT programme is the same for the same HT health status except for the additional RAMP-HT cost.
7. All costs and health preference will be discounted by an annual rate of 3.5% as recommended by the guidance of National Institute for Health and Clinical Excellence (National Institute for Clinical Excellence 2008).

[Word Count: 3968 ]

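### Model assumption 6 sets non-programme medical cost equal in both arms within each health state, so a difference that the study itself measures, in either direction, is left out of the primary ICER

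*Combined protocol and SAP*

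**What the plan says.** All references are to the combined protocol and SAP.

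- **Model.** Assumption 6 in the section on Markov modelling reads: "The medical cost (public and private) of HT patients in usual care and RAMP-HT programme is the same for the same HT health status"; the one exception it allows is the added programme cost. The same section applies an average cost to each disease state, and Table 1 lists direct medical costs by health status without a split by arm.
- **Hypothesis.** Section c, Hypothesis 2, treats the same quantity as open, stating that RAMP-HT patients' medical cost, "for the same disease complication status, is not higher than that of usual care except for the RAMP-HT cost".
- **Measurement.** Direct Medical Costs of HT patients plans extraction of drugs, tests, attendances and admissions for each cohort patient, for the 12 months before baseline and at 12 to 60 months after enrolment. Under Cost Analysis of RAMP-HT, average annual costs "will be analysed by HT complication status (CHD, heart failure, stroke and ESRD), and by RAMP-HT and usual care HT groups".
- **Test.** The same section plans a one-sided t-test of whether RAMP-HT cost is higher. Its wording names the two cohorts and does not repeat the restriction to the same complication status. The sample size section bases 140 per group on showing that RAMP-HT cost is not higher "by independent one side t-test with 0.3 effect size and 80% power at 5% significance level".
- **Programme cost.** This is costed separately as set-up, ongoing intervention (staff, printing, consumables) and central administration. Drugs, laboratory tests, attendances and admissions belong to medical cost.

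The text gives no rule for what the model does if measured costs differ by arm, and no sensitivity analysis of assumption 6.

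**The concern.** The effect side of the model differs by arm: assumption 4 applies the hazard ratio from the cohort analysis to the RAMP-HT arm for the first five years. The state-cost side may not differ. If the programme works partly through more drugs, tests or visits, the ICER credits the benefit and omits that part of what it cost. If the programme reduces other care, the saving is omitted. Either way the primary ICER could disagree with the study's own cost data.

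The complication-free state matters most. On the planning figures (5-year CVD incidence of 7% and 8%), about 93% and 92% of patients would still be free of CVD at five years, before allowing for ESRD and deaths. A modest annual difference in that state is paid for nearly everyone, while the QALY gain comes from the few whose event is avoided.

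**Working it through.** **1. The plan's own figure.** Inputs from the sample size section: effect size 0.3 SD, 80% power, 5% one-sided.

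n per group = 2 × (1.645 + 0.842)² / 0.3² = 137.4, so 138. An exact t calculation gives 139. The stated 140 reproduces, with 80.5% power.

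**2. Could the test justify equality?** Hypothesis 2 says not higher, while assumption 6 says equal, which is stricter. A non-significant one-sided test would establish neither. With the 230 and 218 expected completers of the private-cost survey, one-sided power is:

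| True difference | Power |
|---|---|
| 0.3 SD | 94% |
| 0.2 SD | 68% |
| 0.1 SD | 28% |

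Public cost is available for the full cohorts of 8,681 per arm. There the 95% confidence interval for a difference in means has a half-width of 1.96 × √(2/8,681) = 0.03 SD. For public cost, then, the data can inform the model directly.

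**3. What a difference would do to the ICER.** The documents give no cost difference, cost SD or QALY gain, so this is a range under assumptions.

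- Discount rate 3.5% (assumption 7); duration five years (assumption 4).
- Annuity, first year undiscounted: 1 + 1/1.035 + 1/1.035² + 1/1.035³ + 1/1.035⁴ = 4.673. Discounting from the end of year 1 gives 4.515.
- HK$100 per patient-year × 4.673 = HK$467.
- CVD reduction 8% − 7% = 1 point (sample size section).
- Assumed: 2 to 5 discounted QALYs per CVD case avoided, so a gain of 0.02 to 0.05 QALY per patient.

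Shift in ICER = annual difference × 4.673 / QALY gain.

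| Annual difference | Gain 0.05 | Gain 0.02 |
|---|---|---|
| HK$100 | HK$9,346 | HK$23,365 |
| HK$1,000 | HK$93,462 (32% of threshold) | HK$233,654 (79% of threshold) |

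If all other incremental cost were zero, the difference that alone brings the ICER to HK$295,303 is 295,303 × gain / 4.673: HK$1,264 per patient-year at 0.02 and HK$3,160 at 0.05.

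**4. A larger effect.** The plan calls its 5-year figures conservative. Compounding its 1-year rates gives 1 − (1 − 0.0133)⁵ = 6.5% and 1 − (1 − 0.0176)⁵ = 8.5%, or 2 points. The gain doubles to 0.04 to 0.10, and HK$100 per year moves the ICER by 467/0.10 to 467/0.04, about HK$4,700 to 11,700.

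Two simplifications make these shifts somewhat large: every patient is taken as alive and complication-free for five years, and QALYs from fewer ESRD cases are not counted.

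**The case against.** **The assumption is declared, and much of the cost is kept.** A reader might infer that all extra cost under RAMP-HT is missing. The documents do not support that: the programme cost, including its staff, is added to the RAMP-HT arm, and cost differences arising from time spent in each health state remain. Only within-state differences in non-programme care drop out.

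**The direction is unknown.** A reader might infer that the ICER is biased in favour of RAMP-HT. The introduction reports larger falls in SBP and LDL-C under RAMP-HT but does not say whether more drugs or visits produced them. No figure in the documents shows a cost difference of either sign.

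**Arm-specific cost brings its own bias.** This is the strongest objection, and it stands in part. The cohort is retrospective. The matching covariates include neither prior cost nor prior service use. Usual-care patients must not have enrolled up to 31 March 2017, and being still complication-free is itself a post-baseline condition. Raw arm-specific cost could pass selection differences off as programme effects. The hazard ratio from the same cohorts faces similar threats, and the plan already collects cost for the 12 months before baseline, so adjustment is possible. The objection calls for adjustment and for showing both versions; it does not justify equal cost as the only version.

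**Double counting.** This also stands. RAMP-HT is delivered partly by dieticians, physiotherapists and occupational therapists. Public cost counts those services, and programme cost counts clinic staff. The text does not say whether programme contacts can be identified in the extraction, and the data schema in Appendix F is not in the text reviewed.

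**Conclusion.** The point holds in a limited form. Assumption 6 fixes in advance a quantity that the study measures by arm and state and poses as Hypothesis 2. The primary ICER therefore leaves out any within-state difference in drugs, tests, attendances or admissions, in either direction, and the plan does not say what happens if one is found.

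The size is conditional. Each HK$100 per patient-year over five years moves the ICER by about HK$9,300 to 23,400 per QALY, given the planned 1-point CVD reduction and an assumed 0.02 to 0.05 QALY per patient, and by about half that for a 2-point reduction. This shows that the ICER is sensitive to the assumption. It does not show that a difference exists, that the ICER is wrong, or that arm-specific cost must replace the equal-cost base case.

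**What to change.** Pre-specify a second ICER beside the equal-cost ICER of assumption 6:

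1. For model years 1 to 5, use the arm-specific annual public cost of the complication-free state, estimated in the matched cohorts with adjustment for the baseline covariates and the 12-month pre-baseline cost.
2. Exclude programme contacts from public cost, or net out the programme staff cost, so that nothing is counted twice. State which method the extraction allows.
3. Give a confidence interval for the adjusted difference between arms.
4. Keep pooled costs for the complication states, for private cost (the survey sample is small) and after year 5, when assumption 4 ends the effect.
5. Report both ICERs, and do not conclude that RAMP-HT is cost-effective on the equal-cost version alone if they fall on opposite sides of HK$295,303.

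No cost data beyond the planned extraction are needed, provided programme contacts can be identified in it or the staff cost netted out. The price is some extra analysis, slightly noisier cost inputs and possible residual confounding, to which the hazard ratio is also exposed.
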